There is growing use of soft multifocal contact lenses to slow the progression of myopia in juvenile populations (Walline, Walker, Mutti, et al., 2020). When used for myopia management, the power gradient of a soft multifocal contact lens is utilized to, hypothetically, alter how light focuses in the eye and influence eye growth. Specifically for myopia management, center distance multifocal designs are used. A center distance contact lens optically corrects for the distance refraction in the center of the lens (providing a clear distance image to the macula) while the peripheral portion, with its increasing plus power, generates myopic peripheral defocus. This change in peripheral image focus is thought to provide an optical "stop" signal for axial elongation and myopic progression (Berntsen and Kramer, 2013; Ticak and Walline, 2013; Walline et al., 2020). For myopia management, therefore, multifocal contact lenses are not being used to correct vision or influence accommodation. There have been conflicting reports as to how/if children accommodate normally while wearing multifocal contact lenses. (add some citations here, probably similar to below)

Plus lenses, or add powers, in spectacles are often used in the management of accommodative and binocular vision disorders (Scheiman and Wick, 2008). An add power, or plus lens, relieves accommodative demand. There is conflicting evidence on

whether the add power in soft multifocal contact lenses can be used to manage accommodative and binocular vision disorders (Gong, Troilo and Richdale, 2017; Jimenez, Durban and Anera, 2002; Kang, Fan, Oh, et al., 2013; Madrid-Costa, Ruiz-Alcocer, Radhakrishnan, et al., 2011; Tarrant, Severson and Wildsoet, 2008). Some case reports demonstrate benefits of multifocal contact lenses in accommodative insufficiency and convergence excess but the evidence is not clear and many previous studies utilize lenses that are not readily used anymore (Rodgin, 2009; Weissman, Barr, Harris, et al., 2006). Studies show that soft multifocal contact lenses alter accommodation in participants who wear lenses, but most studies use center-distance lens designs, which is the most commonly used lens for myopia management (Gong et al., 2017; Madrid-Costa et al., 2011; Tarrant et al., 2008).

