Subjective Accommodative Amplitude: This technique quantifies the nearest position of clear focus using a method that is the standard technique used in a routine eye examination whereby the participant will be asked to view a row of 20/30 letters first held in close proximity to the eye (approximately 2-3 cm) and then pulled away from the eye along a near point rod. The participant will be instructed to report the moment when the letters first become blurred. The measurement will be repeated three times and averaged and the individual findings compared to published age norms for classification of reduced or adequate accommodative amplitude (Hofstetter, 1944).

Accommodative Accuracy: This technique determines the accuracy of the eye to focus at a near viewing distance. A handheld light and loose trial spectacle lenses are used to quantify the focusing position of the eye while the participant views letters printed on a card. The lenses are held in front of the participant's eye and the light shown quickly across the eye from arm's length.

Accommodative Facility: This technique determines the ability of the eye to quickly focus and relax, which is often needed for visual demands in a classroom. Participants will view a 20/30 letter at 40 cm. The examiner will then place ± 2.00 D flipper lenses in front of the patient's eye (plus or minus). Once the participant clears the letters, they will state "clear" and the examiner will flip to the other side. The number of flips per minute will be recorded.

Detailed Study Procedures

The study will enroll 20 participants from 18-30 years old. The study consists of two days of office visits to the OSU College of Optometry (a baseline visit, and then a second visit on another day with center-distance and center-near contact lenses). Participants will complete the study visits in the Fry Hall clinic research Lab.

Baseline Exam:

- Questions regarding participant demographics, medical history, ocular history, medication use, and refractive error (glasses and contacts) if known.
- Visual Acuity – participants identifying letters to assess visual acuity at distance and near.
- Contrast Sensitivity – participants identifying letters to identify contrast sensitivity at 50 cm.
- Pupil Size – determination of pupil size using a ruler to measure diameter in millimeters in light and dark.
- Ocular alignment:

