 - Cover Test - participants viewing a letter or picture while an investigator covers the eyes with a cover paddle and assessed eye alignment.

- Modified Thorington - Measured at distance and near.
- Near Point of Convergence – participants viewing letters while they are moved closer to the eyes to assess convergence movements.
- Stereopsis – participants wearing 3D glasses and identifying shapes in a book to assess depth perception.
- Accommodation - Measures of accommodation will be performed in the following order using the protocols described above under “Measurements”:
 - **Push-up method** - Accommodative amplitudes of accommodation will be measured in the right eye only, 3 times.
 - **Monocular estimation method (MEM)** - This will be measured at 40 cm, in the right eye only.
 - **Accommodative Facility** - Accommodative facility (in cycles/minute) will be measured with ± 2.00 D flippers in the right eye only and binocularly.
 - **Grand Seiko WR-5100K** – Refractive Error will be measured at several points:
 - 0 D (distance)
 - 2.5 D (40 cm)
 - 4 D (25 cm)
 - 5 D (20 cm)
- Refractive Error Assessment – Non-cycloplegic central refractive error (with and without contact lenses). Non-cycloplegic refractive error will be assessed with the Grand Seiko WR-5100K. This will be done with and without Biofinity sphere contact lenses (that is the same prescription as the participant’s habitual contact lens prescription). An average of 10 readings will be calculated (both with and without habitual correction).
- Dilation – participants will be dilated with 1% tropicamide. They will receive 2 drops, 5 minutes apart.
- Cycloplegic Central Refractive Error (without contact lenses). Cycloplegic refractive error will be assessed with the Grand Seiko WR-5100K. This will be done without contact lenses on. An average of 10 readings will be calculated.

Second Visit

- At the second visit, participants will repeat measurements completed at the first examination (except for dilation/cycloplegia) with a center-distance and center-near Biofinity multifocal contact lens (both with +2.50 D add). The order will be randomized for each participant. The multifocals will be worn binocularly for all testing except for autorefraction, so that the optics of the contact lenses will not interfere with measurements.

The total time for each study visit will be no more than 90 minutes.

Study Risks

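### Push-up amplitude at visit 2 includes whatever share of the +2.50 D add is in use, so a lens effect can be reported as a difference in accommodation

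*Combined protocol and SAP*

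**What the plan says.** The Measurement section makes accommodation the main outcome and lists four techniques for it: objective amplitude, subjective amplitude, accuracy and facility. None is singled out as primary.

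Of subjective amplitude it says: "This technique quantifies the nearest position of clear focus". It then has "individual findings compared to published age norms for classification of reduced or adequate accommodative amplitude", with no visit specified. Under Baseline Exam, "Accommodative amplitudes of accommodation will be measured in the right eye only, 3 times".

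Under Second Visit, "participants will repeat measurements completed at the first examination (except for dilation/cycloplegia"; the two study lenses are center-distance and center-near, "both with +2.50 D add". The same section adds: "The multifocals will be worn binocularly for all testing except for autorefraction". Push-up, MEM and facility at visit 2 are therefore all done with a multifocal on the tested right eye. The objective measure is arranged differently: the multifocal is on the left eye only, and the right eye, in its distance-only lens, is read.

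Background and Rationale states the mechanism: "An add power, or plus lens, relieves accommodative demand". Data Analysis plans a repeated measures ANOVA over single vision, center-distance and center-near. It does not name the measure to be analysed, allow for the add, or use the reduced/adequate classification.

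**The concern.** The study asks whether accommodation differs between the two designs. A nearest point of clear focus taken through a lens belongs to the eye and lens together. If the lens supplies some of the plus power, the near point moves closer and the amplitude reads higher, although the eye has done nothing more.

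The objective response should move the other way. At a fixed target distance, an eye that is relieved by the add has less left to do, so the right-eye reading falls. Both results carry the name accommodative amplitude, both sit under the main outcome, and no expected direction is given for either. A reader of the results could be told that one design gives more accommodation and also that it gives less. The protocol moves the multifocal off the measured eye for autorefraction because its optics interfere, but has no matching safeguard for push-up or facility.

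**Working it through.** **Inputs from the documents.** Add +2.50 D in both lenses, and multifocals worn for everything but autorefraction (Second Visit). Push-up in the right eye (Baseline Exam). Facility target at 40 cm, that is 1/0.40 = 2.50 D, with ±2.00 D flippers (Measurement). Target difference 0.5 D between designs, SD 0.53 D, 90% power, 14 required, 20 enrolled (Sample).

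**Assumed.** f, the effective share of the add, from 0 to 1. Two-sided alpha of 0.05, since none is stated.

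**1. The plan's own figure.** A paired t-test with difference 0.5 D and SD of the difference 0.53 D gives N = 14 with power 90.3%, so the stated 14 reproduces. At n = 20 the power is 97.9%. The SD comes from an objective measure comparing center-distance with single vision; the documents give no SD for push-up.

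**2. Push-up.** Reading = true amplitude + f × 2.50 D.

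| f | Added to reading, versus single vision |
|---|---|
| 0 | 0 D |
| 0.25 | 0.63 D |
| 0.5 | 1.25 D |
| 0.75 | 1.88 D |
| 1 | 2.50 D |

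For illustration, take an assumed true amplitude of 8 D. The near point is 100/8 = 12.5 cm without the add, 100/9.25 = 10.8 cm at f = 0.5, and 100/10.5 = 9.5 cm at f = 1.

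**3. Contrast between designs.** The two readings differ by (f for center-near − f for center-distance) × 2.50 D, plus any real difference in the eye. An equal share cancels. The difference in f that reproduces the target is 0.5/2.50 = 0.20. With n = 20, a pure lens effect of 0.5 D would be declared significant with this probability:

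| Assumed SD of the paired difference | Power |
|---|---|
| 0.53 D | 97.9% |
| 0.75 D | 80.7% |
| 1.0 D | 56.5% |
| 1.5 D | 29.4% |

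The three-condition ANOVA also includes single vision. Equal shares do not cancel there: f = 0.5 in both designs still separates them from single vision by 1.25 D.

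**4. Opposite directions.** If the eye supplies what the add leaves over, the objective response to a target of demand D is D − f × 2.50. With the same f in both tasks, a design with f larger by 0.20 shows +0.5 D on push-up and −0.5 D on the objective response.

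**5. Facility.** Demand = 2.50 − flipper power − f × 2.50.

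| f | +2.00 D side | −2.00 D side |
|---|---|---|
| 0 | 0.50 D | 4.50 D |
| 0.5 | −0.75 D | 3.25 D |
| 1 | −2.00 D | 2.00 D |

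The minus side becomes easier. The plus side goes below zero, which relaxing accommodation cannot clear through the add zone. The net change in flips per minute has no fixed sign.

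**6. Age norms.** If the classification were applied at visit 2, an eye would move from reduced to adequate only when its own amplitude is below the norm by less than f × 2.50 D. All other eyes keep their class. The norm values are not in the documents, so no count can be given.

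**The case against.** The strongest reply is that function through the lens is a legitimate outcome. Background and Rationale aims to see how accommodative function varies with the lenses and hypothesizes a therapeutic effect. A closer near point alongside a lower objective response is what relief predicts, so it need not be a contradiction. Data Analysis does not pool the measures, and the objective reading is already taken in an eye without the multifocal. All of this stands. It supports keeping the push-up contrast as a difference in clear near range with the lens on. It does not support reading that contrast as a difference in the eye's own accommodation, and the plan does not separate the two.

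Three stronger readings are tempting, and the documents do not support them:

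- A reader might infer that the age-norm classification is wrong at visit 2. No section says it is done there. Accommodative dysfunction is excluded at entry, which gives the comparison an obvious baseline use, and the analysis does not use it. What can be said is that nothing limits it to baseline.
- A reader might infer that facility is inflated in the same way as push-up. The two flipper sides move in opposite senses, and facility has no norm classification in the plan.
- A reader might set the 2.50 D maximum against the 0.5 D target and call it a fivefold bias. The maximum is a multifocal-versus-single-vision figure with the whole add in use, although both designs also carry a distance zone. The target is between two designs with the same add, where only the difference in f remains.

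**Conclusion.** The point holds for push-up. At visit 2 the reading contains 0 to 2.50 D from the lens relative to single vision, depending on f. Between designs, a difference in f of 0.20 is enough to produce the 0.5 D target with no change in the eye. Whether the designs differ by that much cannot be known from the documents, and the chance of declaring such an effect significant depends on a push-up SD that they do not give. Because the objective response would be expected to move the other way and no measure is named as primary, the plan as written leaves open which result answers its question.

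Facility through the lens is a different test from facility in single vision, with no predictable direction of bias. The age-norm issue is a gap in wording with a possible one-sided consequence, not a demonstrated error. These conclusions assume that the add contributes additively as f × 2.50 D and, for the opposite-direction comparison, that f is the same in both tasks.

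**What to change.** 1. State that conclusions about accommodation rest on the objective response read in the eye wearing the single-vision lens. This also matches the objective data behind the sample size. First reconcile two statements under Objective Accommodative Amplitude: that the left eye is patched for all measurements, and that the left eye with the multifocal drives accommodation. Both cannot hold for the same visit 2 reading.
2. Report and analyse visit 2 push-up and facility as through-the-lens functional secondary outcomes. State how visit 2 MEM, also done with the multifocal on, will be interpreted. Give the expected direction of each measure where there is one, and say that facility has none.
3. Limit the age-norm classification to the single-vision baseline push-up.

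The relabelling and the limit on the norms cost wording only and add no measurement. The left-eye statements must be settled before the objective measure can carry the conclusion. The price is that the trial gives up the claim that push-up and facility through a multifocal measure the eye's own accommodation.

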Most studies that have evaluated accommodative ability and function while wearing soft multifocal contact lenses have examined center distance lenses. Because center distance lenses are used for myopia management, the interest has been to determine if children maintain normal accommodative function while wearing the lenses.

Accommodative function while wearing center near lenses has likely not been studied often because these lens designs are used most in presbyopic populations who have no or waning accommodative ability and are using the lenses, specifically, to account for that accommodative inability.-Knowing how spectacle lenses with add powers effectively treat some binocular vision and accommodative disorders and understanding how center near multifocal contact lenses correct presbyopic vision, it is reasonable to hypothesize that center near multifocal contact lenses may provide a greater therapeutic effect for accommodative and binocular vision disorders than center near designs because the central portion of the lens is the addition power, unlike the center-distance lens designs. This study will aim to determine how accommodative function varies with center distance and center near multifocal contact lenses.

Procedures:

Research Design

This study will be an observational single-center investigation using a cross sectional design and each subject will undergo two test sessions.

Sample

The sample size necessary for this study is 20 subjects. The sample size calculation was completed using effect size with standard deviation values from previously published objective accommodative difference between center-distance multifocal contact lenses and single vision contact lenses, which found about $1.0\text{ D} \pm 0.53\text{ D}$ difference (Gong et al., 2017). In order to detect a 0.5 D difference in accommodative amplitude between center-distance and center-near contact lenses with 90% statistical power, a sample of 14 participants is required. Because a study investigating this hypothesis has not been performed in the past, we will enroll an additional 6 patients to account for unknown variability in the data.

Eligibility Criteria are:

- Ages 18 to \leq 30 years old
- Acuity of 20/25 or better in both eyes with habitual contact lens prescription
- No history of ocular disease or active ocular inflammation
- No history of ocular or refractive surgery
- No current history of rigid contact lens wear
- Astigmatism \leq 1.00 D

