The risks involved with the participation of this study are no greater than that incurred in a routine eye exam with dilation. The side effects that participants might experience are blurred vision (that generally affects near viewing more than distance), and light sensitivity. Previous studies suggest that the side effects of both concentrations are minimal and do not impede activities of daily living. These drops will only be instilled one time at one visit and side effects should wear off within 4-6 hours. All other study procedures are non-invasive and only involve lights as the participant places his/her chin on a chinrest and looks straight ahead.

Data Collection and Participant Confidentiality

Data will be collected on a paper study form that includes only the participant's study ID. Study measures obtained with the autorefractor will be printed from the instrument and the participant's study ID written on the print-out. The print-outs will then be taped to the paper study form and later scanned into pdf format for storage on the Investigator's computer. No personally identifying information will be stored on the paper datasheet, or in the generation of the scanned pdf. Signed consent/assent/parental permission documents will be kept separate from the study data sheet in a binder in the Investigator's locked laboratory, accessible only to the study team. The link between the study ID and the participant's personal information will be maintained on the signed consent documents.

Internal Validity

There are no threats to internal validity. All procedures performed in the examination are standard procedures that have been performed frequently in other studies. While this project is assessing measurements in one population, there is limited threat to external validity because this is a project of instrument comparability and repeatability and is not intended to make generalizations about the population as a whole.

Data Analysis

Repeated measures analysis of variance (Repeated measures ANOVA) will be completed with measurement environment (single vision CL, center-distance CL, center-near CL). If differences are detected in lens type (center-distance, o center-near), a post-hoc analysis will take place.

Bibliography:

Berntsen, D.A. & Kramer, C.E. (2013). Peripheral defocus with spherical and multifocal soft contact lenses. *Optom Vis Sci*, 90, 1215-24.

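### Lens order at the second visit has no stated balancing method and the ANOVA has no order term, so any first-to-second shift inflates the error of the center-near versus center-distance contrast

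*Combined protocol and SAP*

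**What the plan says.** Detailed Study Procedures describes two visits: "a baseline visit, and then a second visit on another day with center-distance and center-near contact lenses". Under Second Visit, the baseline measurements (except dilation and cycloplegia) are repeated with each of the two multifocals, within a visit of at most 90 minutes. On sequence, the text says only: "The order will be randomized for each participant". No ratio, block, list or other balancing device appears anywhere.

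Data Analysis gives the whole model: "Repeated measures analysis of variance (Repeated measures ANOVA) will be completed with measurement environment (single vision CL, center-distance CL, center-near CL". If lens types differ, "a post-hoc analysis will take place"; its method is not given. No order, period or sequence term is named. The Internal Validity section sees no threats, so order is not taken up there either.

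The Sample section sizes the study on the two-lens contrast: "In order to detect a 0.5 D difference in accommodative amplitude between center-distance and center-near contact lenses". It then adds a margin: "we will enroll an additional 6 patients to account for unknown variability in the data".

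**The concern.** Each participant goes through a long set of accommodation tests twice in one sitting. Several of the tests depend on effort and response, so results with the second lens could drift from those with the first whichever lens it is. Take center-near minus center-distance within a person. A constant shift is added when center-near comes second and subtracted when it comes first. If order is not in the model, this spread of plus or minus one shift is counted as random error.

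This is a matter of precision, not validity. The stake is a wider interval and lower power on the 0.5 D contrast, plus chance displacement of the estimate when the realised orders are uneven.

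**Working it through.** **Inputs from the documents (Sample section).** Target difference 0.5 D; SD 0.53 D, taken from a published comparison of center-distance multifocal with single vision lenses; power 90%; 14 participants required and 20 enrolled.

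**Assumptions.** Two-sided alpha 0.05 (not stated). The 0.53 D is the SD of the within-person difference and contains no order variation. Shift sizes of 0.10, 0.25 and 0.50 D. Except where balanced order is stated, each participant's order is drawn independently with probability 1/2.

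**1. The plan's own figure.** For a paired t-test with noncentrality (0.5/0.53)·√n, power is 87.7% at n = 13 and 90.3% at n = 14. The stated 14 reproduces, which supports reading 0.53 D as a paired SD. At n = 20 power is 97.9%.

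**2. Effect of a shift π without an order term.** Write the difference for participant i as D = δ + sπ + e, with s = +1 or −1 by order and SD(e) = 0.53. Then SD(D) = √(0.53² + π²):

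- π = 0.10: √(0.2809 + 0.0100) = 0.539 D
- π = 0.25: √(0.2809 + 0.0625) = 0.586 D
- π = 0.50: √(0.2809 + 0.2500) = 0.729 D

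The n for 90% power comes from the noncentral t with these SDs. Power and half-width were simulated at n = 20 (200,000 runs for power, 100,000 for half-width; repeat runs differ by about 0.1 point).

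| Shift (D) | n for 90%, no term | Power, simple randomization, no term | Mean 95% CI half-width, no term (D) | Power, balanced order, no term | Power, balanced order with term |
|---|---|---|---|---|---|
| 0 | 14 | 97.9% | 0.245 | 97.9% | 97.9% |
| 0.10 | 15 | 97.5% | 0.249 | 97.7% | 97.8% |
| 0.25 | 17 | 95.2% | 0.271 | 96.5% | 97.9% |
| 0.50 | 25 | 82.9% | 0.337 | 89.1% | 97.9% |

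Under simple randomization without the term, power is 90.9% at a shift of 0.37 D and 89.9% at 0.39 D. With balanced order and the term, the half-width stays at about 0.245 D at every shift.

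**3. Type I error.** Under simple randomization without the term, a paired test stays near 5% at every shift. Under a forced 10:10 split without the term it falls to 3.1% at 0.25 D and 0.7% at 0.50 D. The estimate is then free of the shift, but its standard error still includes it. With balance and the term it is 5.0% at both shifts.

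**4. Uneven splits.** With 20 independent draws, the chance of exactly 10:10 is 17.6%, of 12:8 or worse 50.3%, and of 14:6 or worse 11.5%. The realised estimate moves by π × (difference in counts)/20. At 14:6 that is 0.4π, or 0.04, 0.10 and 0.20 D for the three shifts. This is part of the wider error already shown, not an additional bias.

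**5. Cost of the term.** With balanced order the error degrees of freedom fall from 19 to 18, and power with no shift is 97.9% either way. Under simple randomization the term gives 97.1% at every shift, a loss of 0.8 points when there is no shift.

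**The case against.** Randomizing the order already deals with the main hazard. A paired comparison of randomly ordered conditions is valid without a period term, so this is a refinement and not an error. The loss also rests on a shift that the documents neither give nor imply. Power falls under the planned 90% only at about 0.39 D, which is 78% of the target difference (0.39/0.5), and the 82.9% figure needs a shift equal to the whole target. The 6 extra participants were added for unknown variability, and 20 exceeds the 17 needed at 0.25 D. The protocol's wording would also fit a balanced list. In that case the unadjusted power at 0.25 and 0.50 D is 96.5% and 89.1%, and a 14:6 split cannot occur. Finally, under simple randomization the term costs a little when the shift is small: 97.5% without it against 97.1% with it at 0.10 D.

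All of this stands, and it is why the point is minor. It does not remove the point. Randomization does not take the shift out of the error. The margin of 6 is better kept for variability that the model cannot remove: a 0.25 D shift uses 3 of the 6 (17 − 14), and a 0.50 D shift needs 25 participants. If a balanced list is intended, the case for the term is stronger, because the test without it is conservative. The calculation covers the dioptric contrast only and shows nothing about facility or the other measures.

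**Conclusion.** The concern holds as a low-priority improvement. The protocol states no allocation method for lens order, and its analysis names no order term, so a constant first-to-second shift would inflate the error of center-near minus center-distance. At n = 20 the loss is about 0.4 points of power at 0.10 D (97.9 − 97.5), 2.7 points at 0.25 D (97.9 − 95.2) and 15.0 points at 0.50 D (97.9 − 82.9). There is no bias on average and, for a paired test, no inflation of type I error.

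These sizes depend on the assumed shifts, alpha and simple randomization, and on 0.53 D being free of order variation. If it already contains some, the loss is smaller.

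**What to change.** State how lens order is allocated, and use a pre-made balanced list: 10 participants with center-distance first and 10 with center-near first. Estimate center-near minus center-distance in a model of the second-visit data with participant, lens and period (first or second lens). Name this as the test of the 0.5 D contrast. Leave single vision out of this model, because it belongs to the baseline visit; the three-level ANOVA can stand beside it. Balance and the term should go together, since balance alone makes the paired test conservative.

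The cost is a list, one additional two-lens model and one error degree of freedom, with no change in sample size. With balance and the term, strict 90% power needs 16 participants in even numbers (89.9% at 14), so 20 is enough. If the orders have already been assigned by simple randomization, the term can still be added wherever order was recorded, at about 0.8 points of power if there is no shift. The term removes only a constant shift; it does not correct one that depends on which lens came first.
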